10.6. Appendix 6: Derived and Transformed Data

10.6.1. General

Multiple Measurements at One Time Point

- If there are two values within a time window the value closest to the target day for that window will be used. If values are the same distance from the target then the mean will be taken.
- Subjects having both High and Low values for Normal Ranges at any post-baseline visits for safety parameters will be counted in both the High and Low categories of “Any visit post-baseline” row of related summary tables. This will also be applicable to relevant Potential Clinical Importance summary tables.

Study Day

- Calculated as the number of days from Day 1 Visit:
 - Ref Date = Missing → Study Day = Missing
 - Ref Date < Date of Day 1 Visit → Study Day = Ref Date – Date of Day 1 Visit
 - Ref Date ≥ Date of Day 1 Visit → Study Day = Ref Date – Date of Day 1 Visit + 1

10.6.2. Study Population

Demographics

Age

- As the month and date of birth will not be collected in the study, the age will be calculated as Year of ICF – Year of Birth;
- Birth date will be presented in listings as ‘YYYY’.

Body Mass Index (BMI)

- Calculated as Weight (kg) / [Height (m)²]

Extent of Exposure

- Duration of exposure to study drug will be calculated based on the formula:
 - The duration of exposure for oral phase is defined as the number of days starting from the first oral dose to the last oral dose.
 - Duration of exposure for injection phase is defined as the number of injections (1, 2, 3, 4 or 5)
 - Overall exposure to CAB is defined as number of days from the first oral dose to 8 weeks following the participant’s last injection. If a participant does not enter the injection phase, the overall CAB exposure for the study will be defined as the number of days from the first oral dose to the last oral dose.
 - Overall exposure to the study (for safety evaluation) is defined as number of days from the first dose to last visit (including unscheduled visit) in days.
- The cumulative dose will be based on the formula:
 - Cumulative dose in oral phase is defined as (number of tablets dispensed – number of tablets returned) * 30 mg

Extent of Exposure

- Cumulative dose in injection phase is defined as number of injections * 600 mg

10.6.3. Safety**Adverse Events****Adverse Events of Special Interest**

- Seizures and seizure like events
- Decline in Renal Function
- Proximal Renal Tubule Dysfunctions
- Proteinuria
- Hepatotoxicity
- Hypersensitivity Reactions
- Injection Site Reactions
- Impact on Creatinine
- Neuropsychiatric Events

The adverse events of special interest that were used for data summaries are provided in Section [10.16](#)

Laboratory Parameters

- HIV-1 RNA: For summaries and analyses which use HIV-1 RNA level as a continuous measure, the logarithm to base 10 of the value will be used.
- If a laboratory value which is expected to have a numeric value for summary purposes, has a non-detectable level reported in the database, where the numeric value is missing, but typically a character value starting with '<x' or '>x' (or indicated as less than x or greater than x in the comment field) is present, the number of significant digits in the observed values will be used to determine how much to add or subtract in order to impute the corresponding numeric value.
 - Example 1: 2 Significant Digits = '< x' becomes $x - 0.01$
 - Example 2: 1 Significant Digit = '> x' becomes $x + 0.1$
 - Example 3: 0 Significant Digits = '< x' becomes $x - 1$

10.7. Appendix 7: Premature Withdrawals & Handling of Missing Data

10.7.1. Premature Withdrawals

Element	Reporting Detail
General	
 Subject study completion (i.e. as specified in the protocol) was defined as completing all phases of the study including week 89. If participants prematurely discontinue the oral phase of the study, additional replacement participants may be recruited at the discretion of the Sponsor. Participants who enter the injection phase of the study will not be replaced All available data from subjects who were withdrawn from the study will be listed and all available planned data will be included in summary tables and figures, unless otherwise specified.

10.7.2. Handling of Missing Data

Element	Reporting Detail
General	
 Missing data occurs when any requested data is not provided, leading to blank fields on the collection instrument: 
 These data will be indicated using a “blank” in subject listing displays. Unless all data for a specific visit are missing in which case the data is excluded from the table. Answers such as “Not applicable” and “Not evaluable” are not considered to be missing data and should be displayed as such. Missing endpoints which are not covered in the following rule will not be imputed, unless otherwise specified.
Outliers	
 Any subjects excluded from the summaries and/or statistical analyses will be documented along with the reason for exclusion in the clinical study report.

10.7.2.1. Handling of Missing Dates

Element	Reporting Detail
General	Partial dates will be displayed as captured in subject listing displays.
Adverse Events	
 Completely missing start or end dates will remain missing, with no imputation applied. Consequently, time to onset and duration of such events will be missing. Partial missing start or end dates will be imputed using the convention specified in Section 10.7.2.2 Handling of Partial Dates

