7.1.2. Adverse Events

Adverse events will be tabulated using MedDRA (v20.0 or above) system organ class (SOC) and preferred terms (PT), or preferred terms alone, by study phase. The number and percentage of participants experiencing each specific AEs (Grade 2 or higher, All AEs, SAEs, AEs leading to permanent treatment discontinuation or study withdrawal) will be tabulated. Number of subjects in the safety population who entered the study phase will be used as denominator in the calculation of percentages.

Drug-related AEs, SAEs, and Grade 2-4 AEs will also be tabulated. Any AE is assumed to be study treatment-related if relationship is marked 'YES' on CRF or value is missing. In addition, a summary table will be created for AEs by maximum severity by study phase. Common AEs are defined as AEs occurring in $\geq 5\%$ subjects during the study (based on preferred term). Common AEs, common non-serious AEs, common Grade 2-4 AEs, and common drug-related Grade 2-4 AEs will be tabulated.

All AE tables will be presented in a decreasing frequency order of SOC or PT unless otherwise specified.

[Table 4](#) provides an overview of the planned AE analyses, with full details of data displays being presented in [Appendix 14](#): List of Data Displays.

Table 4 Overview of Planned AE Analyses

Display Type	Data Displays Generated						
	Stats Analysis			Summary		Individual	
	T	F	L	T	F	F	L
AE Analyses							
All AEs				Y			Y
Grade 2 or higher AEs				Y			Y
SAEs				Y			Y
AE leading to treatment discontinuation or study withdrawal				Y			Y
Drug-related AEs				Y			
Drug-related SAEs				Y			
Drug-related Grade 2 or higher AEs				Y			
Common AEs				Y			
Common non-serious AEs				Y			
Common Grade 2-4 AEs				Y			
Common drug-related Grade 2-4 AEs				Y			

NOTES:

- T = Table, F = Figure, L = Listing, Y = Yes display generated.
- Stats Analysis = Represents TFL related to any formal statistical analyses (i.e. modelling) conducted.
- Summary = Represents TFL related to any summaries (i.e. descriptive statistics) of the observed raw data.
- Individual = Represents FL related to any displays of individual subject observed raw data.

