10.4.2.1. Treatment States for AE Data

Treatment State	Definition
Screening Phase	AE Start Date < Date of First Oral CAB
On-Oral CAB-Treatment	Day 1 ≤ AE Start Date ≤ Date of First CAB LA Injection – 1; for subjects who withdraw from oral CAB treatment, Day 1 ≤ AE Start Date ≤ Withdrawal date + 7 days
On-CAB LA-treatment	Date of First CAB LA Injection ≤ AE Start Date ≤ Date of Week 41 Visit ; for subjects who withdraw from CAB LA injection, Date of First CAB LA Injection ≤ AE Start Date ≤ Date of Last CAB LA Injection + 8 Weeks
Post-Treatment	AE Start Date > Date of Last CAB LA Injection + 8 weeks
Onset Time Since 1 st Dose (Days)	If Date of First Oral CAB (or CAB LA injection) >AE Onset Date, duration = AE Onset Date - Treatment Start Date If Date of First Oral CAB (or CAB LA injection) ≤ AE Onset Date, duration = AE Onset Date - Treatment Start Date +1 Missing otherwise.
AE Duration (Days)	AE Resolution Date – AE Onset Date + 1
Drug-related	If relationship is marked 'YES' on CRF OR value is missing

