10.7.2.2. Handling of Partial Dates

Element	Reporting Detail
Concomitant	
 Partial dates for any concomitant medications recorded in the CRF will be

Element	Reporting Detail
Medications	
imputed using the following convention:
 
 ○ If the partial date is a start date, a '01' will be used for the day and 'Jan' will be used for the month ○ If the partial date is a stop date, a '28/29/30/31' will be used for the day (dependent on the month and year) and 'Dec' will be used for the month. 
 ● The recorded partial date will be displayed in listings.
Adverse Events	
 ● Any partial dates for adverse events will be raised to data management. If the full date cannot be ascertained, the following assumptions will be made: 
 ○ If the partial date is a start date, a '01' will be used for the day and 'Jan' will be used for the month. ○ However, if these results in a date prior to Week 1 Day 1 and the event could possibly have occurred during treatment from the partial information, then the Week 1 Day 1 date will be assumed to be the start date. The AE will then be considered to start on-treatment (worst case). ○ If the partial date is a stop date, a '28/29/30/31' will be used for the day (dependent on the month and year) and 'Dec' will be used for the month, unless this is after the stop date of study treatment; in this case the study treatment stop date will be used. ● The recorded partial date will be displayed in listings.

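### An adverse event with no start date gets no on-treatment state and drops out of the oral- and injection-phase AE tables

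*SAP*

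**What the plan says.** SAP 10.7.2.1 gives the rule for AE dates: "Completely missing start or end dates will remain missing, with no imputation applied". It names one consequence: "Consequently, time to onset and duration of such events will be missing". It says nothing about treatment state or study phase.

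SAP 10.4.2.1 defines four AE states, each as a condition on the start date. Screening is "AE Start Date < Date of First Oral CAB". On oral treatment is "Day 1 ≤ AE Start Date ≤ Date of First CAB LA Injection – 1". On CAB LA is "Date of First CAB LA Injection ≤ AE Start Date ≤ Date of Week 41 Visit". Post-treatment is "AE Start Date > Date of Last CAB LA Injection + 8 weeks". The variants for participants who withdraw change the upper limits but still test the start date. SAP 10.4.1 defines study phases by when an event occurred and offers no substitute when that is unknown.

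SAP 7.1.2 tabulates AEs by system organ class and preferred term, "or preferred terms alone, by study phase". SAP 7.1 restricts the primary safety analysis to events from the first injection to 8 weeks after the last.

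Two neighbouring rules fill gaps in the data. SAP 10.7.2.2 sends partial AE dates to data management. If an unresolved partial start date imputes to before Day 1 but onset on treatment is possible, Day 1 is used: "The AE will then be considered to start on-treatment (worst case)". SAP 7.1.2 and 10.4.2.1 count an AE with missing causality as drug-related.

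**The concern.** The no-imputation rule looks harmless because the SAP links it only to onset time and duration. But the start date is also the only key that places an AE in a treatment state. Without it the event has no column in a by-phase table.

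The result also sits badly with how AEs are collected. Under Protocol 9.2.1, a non-serious occurrence that begins before treatment goes to medical history, not to the AE section. A correctly recorded non-serious AE therefore began on or after the first dose even if its date is unknown, so no state, or a screening state, is the wrong answer for it. Serious events are collected from consent, so this argument does not cover them.

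At stake is an undercount of on-treatment AEs in a primary safety analysis, settled by a programming default that nobody chose in advance.

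**Working it through.** No figure in the plan depends on this rule, so there is nothing to reproduce. The check has two parts.

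**Which state does an undated AE receive?** The four conditions were applied to a missing start date in two ways: as a null, for which every comparison fails, and under SAS ordering, where a missing value sorts below every date (SAP 10.5.3 names SAS). The last column shows a partial date set to Day 1, for comparison.

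| State in SAP 10.4.2.1 | Null | SAS ordering | Partial date set to Day 1 |
|---|---|---|---|
| Screening | false | true | false |
| On oral CAB | false | false | true |
| On CAB LA | false | false | false |
| Post-treatment | false | false | false |

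The undated event has either no state or the screening state. In neither case does it reach the oral, injection or post-treatment column.

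**What is one lost event worth?** Inputs: about 48 participants enter the oral phase and about 40 the injection phase (Protocol 5.2). The denominator is the number in the safety population who entered the phase (SAP 7.1.2). Each participant counts once per category, at highest severity (SAP 7.1).

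- Injection phase: 1/40 = 2.50 percentage points at most.
- Oral phase: 1/48 = 2.08 percentage points at most.

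These are ceilings. A percentage moves only if the participant has no other event in the same category.

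The 5% threshold for common AEs (SAP 7.1.2) is met at 2/40 = 5.0% but not at 1/40 = 2.5%. With 48 as denominator it is met at 3/48 = 6.25% but not at 2/48 = 4.17%. One lost participant could therefore take a preferred term below the line. However, that threshold is defined over the study, not per phase, and the SAP does not say whether an event without a phase enters that count.

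**The case against.** The strongest reply is that the SAP never says these events are excluded; it only leaves their phase unspecified. That is correct: exclusion is an inference from the definitions. It stands as an inference because both ways of evaluating the conditions give it and no other section assigns a phase.

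A reader might infer that the events vanish from every safety output. The documents do not support that. AE listings, including Listing 16 of all AEs (SAP 10.14.10), would show them. The injection site reaction summary takes maximum severity over injection visits (SAP 7.1.1), and the Grade 2 or higher laboratory table is graded from laboratory results (SAP 7.1.3). Neither needs an AE start date.

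A reader might also infer that undated events are the only ones the injection-phase count can lose. That is not so. Under SAP 10.7.2.2 a year-only start date in the year of first dose can be moved to Day 1, which lies in the oral phase, even if the event truly began after an injection. The partial-date rule is conservative about being on treatment, not about the injection phase. The contrast that remains is narrower: partial dates get a query step and an on-treatment default, and completely missing dates get neither in writing.

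Finally, the situation should be rare. AEs are reviewed at every visit from Day 1, a date with even the year known counts as partial, and database cleaning must finish before analysis (SAP 3.2). This limits the size of the problem but does not supply the missing rule.

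**Conclusion.** The point holds as a minor flaw. As written, the SAP's rules leave an AE without a start date out of the oral- and injection-phase AE tables, and so out of the AE part of the primary injection-phase analysis. The effect on the number of participants with on-treatment AEs can only be downward. Its size is at most 2.5 points per affected participant in the injection phase and 2.08 in the oral phase.

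This rests on three assumptions: the definitions in SAP 10.4.2.1 are programmed as written, enrolment is near the planned 40 and 48, and some start dates stay completely missing after cleaning. The documents give no count of such events; few are expected. The documents do not support a claim that the whole primary safety analysis is compromised, or that a serious undated event would go unreported.

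**What to change.** Add to SAP 10.7.2.1, with a matching line in 10.4.2.1, that an AE whose start date is still completely missing after query is counted as treatment-emergent, as follows:

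- in the injection phase, if the participant received at least one CAB LA injection, unless the AE end date precedes the first injection;
- otherwise in the oral phase, unless the AE end date precedes the first oral dose.

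Time to onset and duration stay missing, and affected events are footnoted in the tables.

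Assigning the phase of the visit at which the event was first reported is less suitable. It would place an oral-phase event first reported at Week 5 in the injection phase, and an injection-phase event first reported at Week 53 in follow-up. It also needs an eCRF field that the documents do not confirm.

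The cost is a short addition to the SAP and a small programming change. The downside is that an oral-phase, follow-up or pre-existing event may occasionally be counted in the injection phase; the footnote lets a reader see which events those could be.

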10.7.2.2. Handling of Partial Dates

Element	Reporting Detail
Concomitant	
 Partial dates for any concomitant medications recorded in the CRF will be

Element	Reporting Detail
Medications	
imputed using the following convention:
 
 ○ If the partial date is a start date, a '01' will be used for the day and 'Jan' will be used for the month ○ If the partial date is a stop date, a '28/29/30/31' will be used for the day (dependent on the month and year) and 'Dec' will be used for the month. 
 ● The recorded partial date will be displayed in listings.
Adverse Events	
 ● Any partial dates for adverse events will be raised to data management. If the full date cannot be ascertained, the following assumptions will be made: 
 ○ If the partial date is a start date, a '01' will be used for the day and 'Jan' will be used for the month. ○ However, if these results in a date prior to Week 1 Day 1 and the event could possibly have occurred during treatment from the partial information, then the Week 1 Day 1 date will be assumed to be the start date. The AE will then be considered to start on-treatment (worst case). ○ If the partial date is a stop date, a '28/29/30/31' will be used for the day (dependent on the month and year) and 'Dec' will be used for the month, unless this is after the stop date of study treatment; in this case the study treatment stop date will be used. ● The recorded partial date will be displayed in listings.

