9.2.1. Time Period and Frequency for Collecting AE and SAE Information

- All SAEs will be collected from the signing of the ICF until the final follow-up visit at the time points specified in the SoA ([Section 2](#)).
- All AEs will be collected from the start of treatment until the final follow-up visit at the time points specified in the SoA ([Section 2](#)).

- Medical occurrences that begin before the start of study treatment but after obtaining informed consent will be recorded on the Medical History/Current Medical Conditions section of the case report form (CRF) not the AE section, unless it is an SAE.
- All SAEs will be recorded and reported to the sponsor or designee immediately and under no circumstance should this exceed 24 hours, as indicated in [Appendix 4](#). The investigator will submit any updated SAE data to the sponsor within 24 hours of it being available.
- Investigators are not obligated to actively seek AEs or SAEs in former study participants. However, if the investigator learns of any SAE, including a death, at any time after a participant has been discharged from the study, and he/she considers the event to be reasonably related to the study treatment or study participation, the investigator must promptly notify the sponsor.
- The method of recording, evaluating, and assessing causality of AE and SAEs and the procedures for completing and transmitting SAE reports are provided in [Appendix 4](#).

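### The cap on partial adverse-event stop dates puts the end before the onset for any follow-up-phase event whose stop date stays partial (minor)

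*SAP*

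**What the plan says.** For a partial AE stop date that data management cannot resolve, SAP 10.7.2.2 fills in the last day of the month and, where needed, December, "unless this is after the stop date of study treatment; in this case the study treatment stop date will be used". The concomitant-medication rule in the same table has no such cap. Both RAP versions in the SAP file carry the same AE rule.

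The SAP does not say which date counts as the treatment stop date. Two places come closest:

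- SAP 10.4.2.1 defines the on-CAB LA state as "Date of First CAB LA Injection ≤ AE Start Date ≤ Date of Week 41 Visit", or up to 8 weeks after the last injection for participants who withdraw from injections.
- SAP 10.6.2 has "Overall exposure to CAB is defined as number of days from the first oral dose to 8 weeks following" the last injection.

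Taken literally, it could also be the date of the last injection itself.

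Duration is a defined variable: "AE Resolution Date – AE Onset Date + 1" (SAP 10.4.2.1). SAP 10.7.2.1 treats it as an output of the date rules. Where a date is wholly missing, "Consequently, time to onset and duration of such events will be missing".

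Follow-up events are in scope. Under Protocol 9.2.1, "All AEs will be collected from the start of treatment until the final follow-up visit". SAP 10.4.1 starts the follow-up phase later than 8 weeks after the last injection, and the extended safety analysis in SAP 7.1 uses data from Week 5 to Week 89.

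**The concern.** A cap at the end of treatment makes sense where event collection also ends about then. Here collection continues to Week 89, 56 weeks after the last scheduled injection. In follow-up the cap therefore lies before the event it is meant to close.

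The rule contains no condition that the stop date be on or after the start date, so a programmer who follows it exactly produces an impossible date pair and a zero or negative duration. Follow-up visits are 12 weeks apart (Protocol 5.1), where dates are harder to recall. At stake are the AE duration variable and the analysis end date for these events, and any output that uses either.

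**Working it through.** **Inputs.** Last injection at Week 33, or earlier if injections are discontinued. Follow-up starts more than 8 weeks after it (SAP 10.4.1), so nominally after Week 41, and runs to Week 89. Duration = resolution date - onset date + 1 (SAP 10.4.2.1). The plan gives no figure of its own to reproduce.

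**Step 1: does the cap always apply in follow-up?** For an AE with a follow-up onset:

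imputed stop (end of month or year) ≥ true stop ≥ onset > last injection + 8 weeks ≥ treatment stop date.

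The imputed stop is always later than the cap, so the cap always applies. The capped stop is always earlier than the onset.

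**Step 2: size with the cap at Week 41.** An onset k days after the cap gives a duration of 1 - k. Follow-up has (89 - 41) × 7 = 336 nominal onset days. One of them (k = 1) gives 0, and the other 335 are negative.

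| Onset | Arithmetic | Duration (days) |
|---|---|---|
| Week 53 | (41 - 53) × 7 + 1 | -83 |
| Week 65 | (41 - 65) × 7 + 1 | -167 |
| Week 77 | (41 - 77) × 7 + 1 | -251 |
| Week 89 | (41 - 89) × 7 + 1 | -335 |

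**Step 3: size with the cap at the last injection.** An AE starting 1 to 56 days after the last injection is still in the injection phase. If its stop date is partial, it also ends before it starts, with a duration from 1 - 1 = 0 to 1 - 56 = -55. Follow-up onsets begin at day 57, where the duration is 1 - 57 = -56 and falls from there.

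**Step 4: illustration with assumed dates.** Last injection 2 June 2019, so last injection + 8 weeks is 28 July 2019. An AE starts on 20 October 2019 (20 weeks after the last injection, nominal Week 53), and its stop is recorded only as October 2019. The imputed stop of 31 October is cut back to 28 July. That is 84 days before onset, so the duration is -84 + 1 = -83.

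**Step 5: enumeration.** The rule was applied to 730 Day 1 dates × 5 possible numbers of injections × 48 weekly follow-up onsets × 4 true durations = 700,800 cases. In all 700,800 the stop fell before the start. This held whether the day alone or the day and month were missing, and for each of three readings of treatment stop. The largest duration was 0 (last injection + 8 weeks), -56 (last injection) or -63 (last oral dose).

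**Step 6: start date also partial.** Start imputation can move a true follow-up event into an earlier phase, and the inversion is then not guaranteed. With both dates known only to the year, five injections and the cap at the last injection, 56,543 of 122,640 true follow-up cases kept a follow-up start under the SAP. All 56,543 were inverted.

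**The case against.** The strongest reply is that little in the planned output can be shown to be wrong. Partial dates go to data management first, so the rule meets only what remains. Phase is assigned from the start date, so the stop-date cap moves no event between phases. Listings show the partial date as recorded. No display title in SAP 10.14 mentions duration, and the table shells are available only on request (SAP 10.15). Whether a display such as Table 2.17, on characteristics of AEs of special interest, uses duration cannot be told from the documents. All of this stands, and it limits the severity. It does not rescue the rule, which gives an impossible result whenever it is applied to a follow-up-phase event.

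Two stronger readings are tempting, and the documents do not support them.

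- **That every follow-up AE is corrupted.** Complete stop dates are untouched, and wholly missing ones stay missing (SAP 10.7.2.1). Only partial stop dates left unresolved are reached.
- **That the start-date rule biases the CAB LA analysis by sending ambiguous events to the oral phase.** The rule is explicit and deterministic: "If the partial date is a start date, a '01' will be used for the day and 'Jan' will be used for the month", and if that falls before Day 1 while on-treatment onset is possible, "then the Week 1 Day 1 date will be assumed to be the start date". A start compatible with both phases does go to oral. The same rule also pulls follow-up onsets back into the injection phase. With the day missing and onsets assumed even over the calendar, about 14.7 injection-phase days move out at the front and about 14.7 follow-up days move in at the back. The net direction is not established. Sending ambiguous starts to CAB LA instead would misplace others: about 48% of day-missing events in the first-injection month would truly be oral-phase. This is a choice between conventions and not an error.

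**Conclusion.** The stop-date cap is wrong as written for AEs that have a follow-up-phase start date under the SAP and a partial stop date left unresolved after the query. Each is given an end before its onset and a duration of 0 or less, down to -335 days with the cap at Week 41. If treatment stop means the last injection, events starting in the following 8 weeks fail as well.

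The result assumes that the treatment stop date is no later than 8 weeks after the last injection. The SAP's exposure definition fits this. A small exception is possible if the cap is the actual Week 41 visit and that visit falls late within its ±3-day window: an onset between last injection + 8 weeks and the visit need not be inverted. The day counts in the table use the nominal schedule.

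The number of events affected cannot be estimated from the documents and may be small. Severity is minor: a derived variable is wrong, with no shown effect on event counts, phase assignment or the primary safety tabulation.

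**What to change.** Replace the cap in the AE row of SAP 10.7.2.2 with:

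*If the imputed stop date is after the last study contact date, use the last study contact date, within the recorded month/year and never before the AE onset date.*

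State that onset means the recorded date or, if that is partial, the date imputed by the existing start rule, so that the start is settled first. Define last study contact. SAP 10.6.2 already uses the last visit, including unscheduled visits, for overall study exposure, and that date could serve. In the illustration above, with a later last contact, the stop becomes 31 October and the duration 31 - 20 + 1 = 12 days.

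The start-date rule can stay. Optionally, footnote the by-phase AE tables with the number of AEs whose phase rests on an imputed start date, so that readers can see whether the convention matters.

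The cost is one SAP sentence with its two short definitions, a small programming change and, if wanted, one footnote. No new data or visits are needed.
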